| 
 
○ %CD4 (Helper Cells) / %CD8 (Suppressor T Cells)
 
• Quantitative immunoglobulin concentration (IgA, IgG, IgM)
 
 
4) Clinical Status – assessed by the following parameters:
 
 
• Infections: Clinically documented and microbiologically documented;
 
• Hospitalizations: Incidence and duration of hospitalizations through completion of the EZN-2279 treatment period compared to the 6-month period prior to study entry;
 
• Growth: Height-for-age and weight-for-age Z-scores through completion of the EZN-2279 maintenance period;
 
• Overall survival: will be assessed at the conclusion of the EZN-2279 treatment period though the end of EZN-2279 maintenance
 
 
The secondary endpoints for assessment of safety are:
 
 
1) Safety will be assessed through determination of adverse events (AEs), serious adverse events (SAEs), physical examinations, and laboratory evaluations through completion of the EZN-2279 maintenance period.
 
2) Immunogenicity of EZN-2279 and Adagen® will be assessed through the end of the EZN-2279 maintenance period by the evaluation of binding antibodies, neutralizing antibodies and anti-PEG antibodies.
 
 
The pharmacokinetic endpoint is the PK profile of EZN-2279, as assessed by plasma ADA activity. The following PK parameters will be computed from individual plasma concentrations collected during full PK sampling for Adagen® at the end of the Adagen® Lead-in period and for EZN-2279 during Week T-9 (after 9th dose of EZN-2279): Cmax, Ctrough, tmax, AUC(0-t), Kel, and t1/2.
  |                                |   |
| Study Design and Methodology:   |                                |   |

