Results of the pharmacology and PD studies performed in the ADA-/- mouse model suggest EZN-2279 behaves very similarly to Adagen® and both compounds are highly effective. Consistent with this, when Adagen® and EZN-2279 were given at equivalent doses and schedules, both PEG-ADA compounds 1) were delivered to the circulatory system with equal efficiency in both ADA+/+ and ADA-/- mice; 2) increased ADA plasma levels to similar, clinically relevant levels; 3) decreased abnormally high adenosine levels found in the lung, spleen, or thymus to a similar extent; 4) maintained thymus and spleen cellularity, including total cell numbers and T- and B-cell populations; and 5) promoted the survival of ADA-/- mice. There is a suggestion that EZN-2279 may be more efficacious than Adagen® in the ADA-/- mouse model. The results tended to show EZN-2279-treated ADA-/- mice having statistically lower adenosine levels in the thymus compared with Adagen®, as well as a consistent trend toward better improvement of most PD endpoints (body weight, survival, and thymocyte and splenocyte cell number, as well as adenosine levels in spleen) when compared with Adagen®. These effects correlated with 35% higher plasma levels of ADA activity derived from EZN-2279 compared with Adagen® when analyzed either 24 or 72 hours after the last dose; the higher plasma levels of ADA activity are likely due to the longer half-life of EZN-2279.

The rarity of patients with ADA-deficient combined immunodeficiency precludes a randomized controlled study; however, as described, each patient will serve as his or her own control. Monitored treatment of patients with Adagen® before EZN-2279 allows a direct comparison of an equivalent starting dose in these patients regarding changes in body weight as percentile on the growth curve, metabolic detoxification, lymphocyte subsets, antibody formation, etc.

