#### 6.3.2. Secondary Endpoints

The secondary endpoints for efficacy are:

- Trough Plasma ADA Activity - will be assessed from trough plasma ADA samples obtained at Weeks T-15, T-17, T-19, and T-21. Adequate trough ADA activity will be defined as ADA activity  $\geq 15 \mu\text{mol/h/mL}$ .
- Maintenance phase trough plasma dAXP and ADA activity - will be assessed from trough plasma dAXP and ADA samples obtained during the maintenance phase of the study through completion of EZN-2279 treatment
- Immune Status – will be assessed through completion of the EZN-2279 maintenance period, through assessment of:
  - Absolute lymphocyte count
  - B-, T-, and NK-lymphocyte subset analysis: The number of cells for each subset will be determined by FACS using the following panel:
    - CD3+ (Mature T cells)
      - Percent and Absolute
    - CD3+ CD8+ (Suppressor T Cells)
      - Percent and Absolute
    - CD3+ CD4+ (Helper Cells)
      - Percent and Absolute
    - CD (16+56)+ (Natural Killer Cells)
      - Percent and Absolute
    - CD19+ (B Cells)
      - Percent and Absolute

- Absolute Lymphocytes (CD45+)
- %CD4 (Helper Cells) / %CD8 (Suppressor T Cells)
- Quantitative immunoglobulin concentration (IgG, IgA, IgM)
- Clinical status – will be assessed through determination of the following parameters
  - Infections through completion of the EZN-2279 treatment period will be determined and defined as either:
    - Clinically documented – patients with documented signs and symptoms of infection without positive microbiologic cultures
    - Microbiologically documented – patients with documented signs and symptoms of infection and with positive viral or bacterial cultures
  - Hospitalizations – Incidence and duration of hospitalizations through completion of the EZN-2279 treatment period compared to the 6-month period prior to study entry
  - Growth – height, weight and growth curve determinations through completion of the EZN-2279 maintenance period
  - Overall survival – will be assessed at the conclusion of the EZN-2279 treatment period through the end of EZN-2279 maintenance

The secondary endpoints for safety are:

- Safety – will be assessed through determination of adverse events (AEs), serious adverse events (SAEs), physical examinations, laboratory evaluations, and immunogenicity through completion of the EZN-2279 maintenance period.

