#### 10.5.3.3. Growth

Height (in cm) and weight (in kg) will be obtained for determination of height-for-age and weight-for-age Z-scores.

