### 13.2.3. Data Analysis

Statistical analysis will be conducted by Leadiant Biosciences, or its designee. The primary analysis of study data will be performed after the last patient has completed through the EZN-2279 treatment phase (Study Week T-21). Once the last patient enters the EZN-2279 maintenance phase, data will be analyzed after all patients complete 6-months of EZN-2279 maintenance (EZN-2279 treatment week 47) and annually thereafter. The analysis of study data will be repeated upon study completion.

Efficacy and safety analyses will be performed using Statistical Analysis Systems® (SAS®) Version 9 or later (SAS Institute, Cary, NC), or comparable software.

A complete description of data handling rules and planned statistical analyses is detailed in a separate Statistical Analysis Plan (SAP). Unless otherwise specified in this document or in the SAP, baseline is defined as the last measurement for a variable before the initial dose of study drug (EZN-2279 or Adagen®), and missing data will generally not be imputed. If applicable, hypotheses will be tested at a two-sided statistical significance level of 0.05.

Analyses will be primarily descriptive, with data listings, graphical presentations, frequency tabulations, and summary statistics as appropriate.

Each patient will serve as his/her own control based on the baseline assessment of each endpoint as appropriate, including changes in body weight as percentile on the growth curve, antibody formation, etc.

Additional statistical analyses, other than those described in this section, may be performed if deemed appropriate to further explore the study data.

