### 13.2.3.4. Efficacy Data Analysis

- Primary Efficacy Endpoint – the primary efficacy endpoint is the percentage of patients achieving metabolic detoxification, defined as achieving and maintaining the target trough total erythrocyte dAXP concentration of  $\leq 0.020$   $\mu\text{mol/mL}$  while receiving EZN-2279. Total erythrocyte dAXP from a trough blood sample will be evaluated at various timepoints (see Appendix 2 for collection schedule).
- Secondary Efficacy Endpoints – Analyses of the following secondary efficacy endpoints will be primarily descriptive, with data listings, graphical presentations, frequency tabulations, and summary statistics as appropriate.
  - Trough plasma ADA activity: the percentage of patients achieving and maintaining the target trough plasma ADA activity of  $\geq 15$   $\mu\text{mol/h/mL}$  while receiving EZN-2279
  - Immune function status:
    - Absolute Lymphocyte count
    - B-, T-, and NK-lymphocyte subset analysis: the number of cells for each subset will be determined by FACS. The following subsets will be assessed:
      - CD3+ (Mature T cells) - Percent and Absolute
      - CD3+ CD8+ (Suppressor T Cells) - Percent and Absolute
      - CD3+ CD4+ (Helper Cells) - Percent and Absolute
      - CD (16+56)+ (Natural Killer Cells) - Percent and Absolute
      - CD19+ (B Cells) - Percent and Absolute
      - Absolute Lymphocytes (CD45+)
      - %CD4 (Helper Cells) / %CD8 (Suppressor T Cells)
    - Quantitative immunoglobulin concentration (IgA, IgG, IgM)
  - Infections: Clinically documented and microbiologically documented
  - Incidence and duration of hospitalizations
  - Growth: Height-for-age and weight-for-age Z-scores
  - Overall survival

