6.3.4 Clinical Status

Clinical status will be assessed through the conclusion of the EZN-2279 maintenance treatment period, through assessment of:

- Infections determined and defined as either:
 - Clinically documented – patients with documented signs and symptoms of infection without positive microbiologic cultures
 - Microbiologically documented - patients with documented signs and symptoms of infection and with positive viral or bacterial cultures
- Hospitalizations - incidence and duration of hospitalizations
- Change in growth – height, weight and growth curve determinations while patients are 18 years of age and younger
- Overall survival – through the EZN-2279 maintenance phase

The total number of infections and the incidence and duration of hospitalizations during the EZN-2279 treatment period will be summarized. Summary statistics for height, weight and BMI percentiles will be presented at baseline, each intermediate collection time-point, and endpoint. Percentiles will be calculated programmatically based on reported age, gender, height and weight.¹ Percentile scores and changes from baseline of percentile scores to each visit (at which height and weight are assessed) and endpoint will be summarized using descriptive statistics.

The proportion of patients surviving through the EZN-2279 maintenance phase will be summarized.

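### The SAP summarises growth only as percentiles, while the protocol's synopsis and planned efficacy analysis specify Z-scores; the change of scale is not declared and can distort mean change if some children start well below the median.

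*SAP*

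**What the plan says.** The protocol names Z-scores in four places. The synopsis (Section 2) lists among the secondary endpoints "Growth: Height-for-age and weight-for-age Z-scores through completion of the EZN-2279 maintenance period", and names the same Z-scores again among its efficacy variables. Section 10.5.3.3 says that height and weight "will be obtained for determination of height-for-age and weight-for-age Z-scores". Section 13.2.3.4, which sets out the efficacy analysis, has "Growth: Height-for-age and weight-for-age Z-scores".

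Other parts of the protocol differ. Section 6.3.2 gives the growth endpoint as "height, weight and growth curve determinations through completion of the EZN-2279 maintenance period", with no scale. Section 13.2.3 describes each patient as his or her own control, "including changes in body weight as percentile on the growth curve, antibody formation, etc". Section 5.4 likewise speaks of "changes in body weight as percentile on the growth curve".

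SAP 6.3.4 follows the wording of protocol 6.3.2 in its list of measures and limits growth to patients aged 18 or younger. It then plans summaries of height, weight and BMI percentiles at baseline, each intermediate time point and endpoint. The change measure is "Percentile scores and changes from baseline of percentile scores to each visit" and endpoint. SAP 5.3 also uses percentiles at screening. Z-scores appear nowhere in the SAP text; its mock displays are in a separate document that is not available here. SAP 6.1 covers only the timing of interim and final looks.

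**The concern.** There are two problems. The first is traceability: the protocol section that specifies the growth analysis names one measure, the SAP computes another, and the SAP section meant to record such changes does not mention it. BMI percentiles are added in the same silent way.

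The second is the scale. A percentile is a rank, not an equal-interval measure, so the same gain in SD units moves it a lot near the median and very little in the low tail. Averaging percentile changes over children with different starting points mixes units that are not comparable. Growth status is a stated secondary objective (protocol 6.2.2, SAP 2.2). SAP 6 plans no statistical testing, so the descriptive summary is the whole result for that objective. If some children start low, the summary could understate their gain or loss, or be driven by whichever child sits nearest the median.

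**Working it through.** **Inputs.** The documents state no growth effect, SD or baseline value, and the sample size of six (SAP 3.2) has no formula behind it. There is therefore no plan figure to reproduce. Starting Z and size of gain are assumptions, shown over a range: starts from -3 to 0, and gains of 0.25, 0.5 and 1.0 SD.

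**Formula.** Percentile = 100 × Φ(Z), so the change for a gain d from start s is 100 × [Φ(s + d) − Φ(s)].

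**Worked lines for d = 0.5.**
- From Z = 0: 69.15 − 50.00 = 19.15 points.
- From Z = -1: 30.85 − 15.87 = 14.99 points (from unrounded values).
- From Z = -2: 6.68 − 2.28 = 4.41 points (from unrounded values).
- From Z = -3: 0.62 − 0.14 = 0.49 points (from unrounded values).

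On the Z scale each of these is 0.50.

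**Full range.** Change in percentile points, with the share of the change seen from a start at the median in brackets:

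| Start Z | gain 0.25 SD | gain 0.5 SD | gain 1.0 SD |
|---|---|---|---|
| 0 | 9.87 (100%) | 19.15 (100%) | 34.13 (100%) |
| -0.5 | 9.28 (94%) | 19.15 (100%) | 38.29 (112%) |
| -1 | 6.80 (69%) | 14.99 (78%) | 34.13 (100%) |
| -2 | 1.73 (17.5%) | 4.41 (23%) | 13.59 (40%) |
| -2.5 | 0.60 (6.1%) | 1.65 (8.6%) | 6.06 (18%) |
| -3 | 0.16 (1.7%) | 0.49 (2.5%) | 2.14 (6.3%) |

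For starts between Z = -1 and 0 the shares run from 69% to 112%, so the compression is mild. At Z = -2 or below they run from 40% down to 1.7%.

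**Effect on a mean over six patients (assumed example).** Starts are -3, -3, -2.5, -2.5, -2 and 0. The first five gain 0.5 SD and the last loses 0.5 SD.
- Mean Z change = (5 × 0.5 − 0.5) / 6 = +0.33.
- Percentile changes are 0.49, 0.49, 1.65, 1.65, 4.41 and −19.15. Their sum is 8.69 − 19.15 = −10.46, and the mean is −10.46 / 6 = −1.7 points.

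The sign of the mean reverses. The median percentile change, (0.49 + 1.65) / 2 = 1.07, stays positive but is small, although five of the six children gained half an SD. The example shows what can happen; it does not predict this trial's data.

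**The case against.** The strongest reply is that the SAP follows wording the protocol also contains. Protocol 6.3.2 names no scale, and 5.4 and 13.2.3 refer to percentiles. A reader might infer that the protocol uniformly requires Z-scores and that the SAP simply departs from it; the documents do not support that. Even so, the percentile passages are general illustrations, concern body weight only, and say nothing of height or BMI. The section that lists the efficacy analyses says Z-scores. The inconsistency explains the SAP's choice, but it does not remove the need to declare it.

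A second reply is that these children may not be small. This stands as a limit on the point. Protocol 5.1 lists failure to thrive as a feature of the disease, and a reader might infer that enrolled patients lie in the low tail. But entry requires stable clinical status on Adagen and a dose stable for at least 6 months (protocol 9.2), and no growth criterion or baseline growth value is given.

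A third reply is that little depends on the summary. Growth is one part of a secondary endpoint, and nothing is tested. SAP 6 lists all efficacy data, and SAP Appendix C plans patient profiles. SAP 11 provides for medians and ranges as well as means. With about six patients, growth can be read child by child. This limits the harm, but the SAP text plans no Z-score derivation, so the listings would not necessarily show the protocol's measure.

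**Conclusion.** The point holds, with limited impact. The mismatch between the SAP and protocol Sections 2, 10.5.3.3 and 13.2.3.4 is plain from the text, as is the absence of any declaration in SAP 6.1. The compression is arithmetic, given a normal reference scale. Its size in this trial is unknown: a 0.5 SD gain would show as 78% to 100% of the median-start change for starts between Z = -1 and 0, as 23% at Z = -2, and as 2.5% at Z = -3.

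Two stronger readings should be resisted. One is to quote only the extreme contrast: a 1 SD gain is 2.14 points from Z = -3 but 38.29 from Z = -0.5, a ratio of 17.9. No document places patients at Z = -3 or predicts a 1 SD gain, and from Z = -1 the same gain is 34.13 points. The other is that a conclusion of the trial is at risk. No decision rule, test or sample size rests on growth, so the effect is confined to the growth objective. Because starting points are unknown, the sound choice is the scale that reads the same at every start, and the protocol already names it.

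**What to change.** In SAP 6.3.4, summarise height-for-age and weight-for-age Z-scores and their change from baseline at each visit and at endpoint, for patients aged 18 or younger. Compute them from the age, gender, height and weight that the section already names as inputs. Keep the percentile summaries as a supplement, so that the body-weight percentile in protocol 5.4 and 13.2.3 is still reported.

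Align protocol 5.4, 6.3.2 and 13.2.3 with the synopsis, 10.5.3.3 and 13.2.3.4, so that one growth scale is primary throughout. If the sponsor prefers percentiles alone, SAP 6.1 should declare and justify that change.

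The cost is a small programming and table change plus a few lines of text. No new data, visits or measurements are needed.

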6.4 Interim Analyses

As noted in Section 3.1, the initial three patients will be enrolled and complete through full EZN-2279 pharmacokinetic sampling (Week T-9). An independent data and safety monitoring committee (DSMC) will review safety, PK (ADA activity), and erythrocyte dAXP data.

¹ <http://www.cdc.gov/nccdphp/dnpao/growthcharts/resources/sas.htm>

If no concerns are noted, enrollment will continue for the remaining three patients. A similar DSMC review will occur after all six patients complete through 9-weeks of EZN-2279 dosing.

Interim data will be used for a BLA when three subjects have complete data through week T-21. The BLA will include all patients enrolled at that time. Details of this analysis will be described in the BLA Statistical Analysis Plan.

7. SAFETY ANALYSIS

The as-treated population will be used for all of the safety analyses. Summaries will be presented by study drug group (EZN-2279 or Adagen[®]), if appropriate, through completion of the EZN-2279 maintenance period. All safety data will be listed.

7.1 Changes to the Planned Safety Analysis Proposed in Protocol

The protocol called for interim analyses when three patients will be enrolled and complete through full EZN-2279 pharmacokinetic sampling (Week T-9) and again when six patients complete through 9-weeks of EZN-2279 dosing. There will be a third look that will be used for a BLA. In addition, there will be a final analysis (fourth analysis) on subjects who complete one year (two maintenance cycles).

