## 7.4. Study Duration

The primary analysis of data for efficacy, PK, immunogenicity, clinical status, and safety will be performed when the Week T-21 (at least 21 weeks of EZN-2279 treatment) data is available for the last patient enrolled in the study.

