#### **11.4. EZN-2279 Maintenance Period**

As part of standard clinical care, the following evaluations will be performed during visits approximately every 3 months (13 weeks  $\pm$ 3 weeks) until study completion. For example, based upon the start of EZN-2279 treatment (Day 1, Week T-1), maintenance visits would be scheduled to occur on Weeks 34 (Cycle 1), 47 (Cycle 2), 60 (Cycle 3), 73 (Cycle 4), 86 (Cycle 5), 99 (Cycle 6), 112 (Cycle 7), 125 (Cycle 8), 138 (Cycle 9), 151 (Cycle 10), 164 (Cycle 11), 177 (Cycle 12), 190 (Cycle 13)  $\pm$ 3 weeks from start of EZN-2279 treatment.

The patient will have the following procedures performed at each maintenance visit prior to EZN-2279 dosing:

- Physical examination
- Height and weight for growth assessment
- Performance status
- Vital Signs
- Safety Lab
  - Hematology
  - Chemistry
  - Urinalysis
- Other labs – blood samples will be obtained 15 to 30 minutes prior to dosing for:
  - dAXP
  - Trough ADA activity
  - B-, T-, and NK-lymphocyte subset analysis
  - Quantitative immunoglobulins
  - EZN-2279 antibody titers (i.e., neutralizing and binding antibodies) and anti-PEG antibodies
- Adverse event assessment
- Assessment of infectious complications and hospitalizations
- Review of EZN-2279 administration diary card and returned vials for assessment of treatment compliance
- Assessment of concomitant medications and procedures since last study visit

- Assessment of overall survival

An appropriate supply of EZN-2279 will be dispensed along with a medication compliance diary card. Note that it is not necessary to dispense a full 13 week supply during a maintenance visit; quantities of EZN-2279 dispensed will be at the discretion of the Investigator based upon the patient's proximity to the study site and medication compliance.

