6.1 Changes to the Planned Efficacy Analysis Proposed in Protocol

The protocol called for interim analyses when three patients will be enrolled and complete through full EZN-2279 pharmacokinetic sampling (Week T-9) and again when six patients complete through 9-weeks of EZN-2279 dosing. There will be a third look that will be used for a Biologics License Application (BLA). In addition, there will be a final analysis (fourth look) to be completed on all patients on EZN-2279 after one year (i.e. two maintenance cycles).

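### SAP 7.1 words the final safety analysis as one on subjects who complete one year, which contradicts the as-treated rule and permits a completer-only reading; the list of looks also omits the T-21 primary, annual and study-completion analyses

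*SAP*

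**What the plan says.** **Who is analysed.** SAP 7.1 closes its list of looks with: "there will be a final analysis (fourth analysis) on subjects who complete one year (two maintenance cycles"). SAP 7 states without qualification: "The as-treated population will be used for all of the safety analyses". SAP 4.1 defines that population as everyone enrolled who received at least one dose of EZN-2279 or lead-in Adagen. SAP 6.1 describes the same look differently: "there will be a final analysis (fourth look) to be completed on all patients on EZN-2279 after one year". SAP 6 uses the as-treated set for non-primary efficacy unless otherwise noted, which covers survival. The survival rule in SAP 6.3.4 is: "The proportion of patients surviving through the EZN-2279 maintenance phase will be summarized". It gives no denominator.

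**When.** SAP 6.1 and 7.1 list four looks: three patients at Week T-9, six at T-9, a BLA look, and the one-year look, which they call final. SAP 10.1 also ties the final analysis to one year. The protocol plans more. Section 7.4: "The primary analysis of data for efficacy, PK, immunogenicity, clinical status, and safety will be performed when the Week T-21" data are available for the last patient enrolled. Section 13.2.3 adds an analysis at Week 47, annual analyses after that, and: "The analysis of study data will be repeated upon study completion".

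**What one year means.** SAP 6.1, 7.1 and 10.1 equate it with two maintenance cycles. Protocol 11.4: "maintenance visits would be scheduled to occur on Weeks 34 (Cycle 1), 47 (Cycle 2"), with a window of three weeks either side.

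**The concern.** The one-year sentence is the most specific statement in the SAP about the final safety analysis, and it stands under a heading on changes to the planned analysis. A programmer could reasonably take it to override the general as-treated rule. Restricted to one-year completers, survival to that point would be 100% and discontinuation for an adverse event 0% by construction. With six evaluable patients, one person moves the percentage by about 17 points.

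Timing is the second issue. EZN-2279 is a long-term replacement therapy, and SAP 6.3.2 to 6.3.4 and 7 define trough levels, immune status, clinical status, survival and safety through the end of maintenance. A look called final at Week 47 cannot deliver those summaries, and no later look is listed. The primary analysis also has no stated trigger in the SAP.

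**Working it through.** **1. The plan's own figure: one year equals two maintenance cycles.** From the protocol 11.4 calendar, visit week = 21 + 13 × cycle.
- Cycle 2: 21 + 26 = Week 47; 47 × 7 = 329 days; 329/365.25 = 0.90 year.
- Window of ±3 weeks: Week 44 (0.84 year) to Week 50 (0.96 year).
- If the window applies per 13-week interval, as the schedule footnote can be read, the upper end is 47 + 6 = Week 53.
- If Weeks T-5 to T-8 are repeated after a dose adjustment (protocol 11.3.8.1), Cycle 2 moves by four weeks to about Week 51 (48 to 54).

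The figure is not reproduced on the nominal calendar. Protocol 13.2.3 calls the same point six months of maintenance (21 + 26 = 47), while protocol 7.7 calls it one year in describing a DSMC review.

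**2. Looks side by side.**

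| Analysis | Protocol | SAP 6.1 / 7.1 | SAP 10.1 |
|---|---|---|---|
| All patients at T-21 (primary) | 7.4, 13.2.3 | not listed | DSMC review only |
| Week 47 | 13.2.3 | yes, as one year and final | DSMC review; also named as the final analysis |
| Annual | 13.2.3 | not listed | not listed |
| Study completion | 13.2.3 | not listed | not listed |
| BLA | 13.3 plans an interim once three patients complete T-21 | third look; 6.4 triggers it at three subjects through T-21 | three subjects through one year |

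**3. Effect of a completer-only denominator.** These are illustrations with exact 95% intervals.
- One death after T-21 and before Week 47, six treated, no replacement: as-treated survival 5/6 = 83.3% (35.9 to 99.6%); completers 5/5 = 100% (47.8 to 100%).
- Two such deaths: 4/6 = 66.7% (22.3 to 95.7%) against 4/4 = 100% (39.8 to 100%).
- One death before T-21, with replacement under protocol 9.5.3, so seven treated: deaths 1/7 = 14.3% (0.4 to 57.9%) against 0/6 = 0% (0 to 45.9%).

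The documents give no early-loss rate. For an assumed per-patient risk d, the chance of at least one loss among six is 1 − (1 − d)^6: 11%, 26%, 47% and 74% for d = 2%, 5%, 10% and 20%.

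**4. Exposure beyond the look called final.** Protocol 7.4.1 gives about three years of treatment for the first patient, about two for the last, and 12 months of enrolment. Take 156 and 104 weeks, with even entry.
- Planned total: 6 × 130 = 780 patient-weeks (14.9 patient-years).
- Cut at the last patient's Week 47: all patients stop at the same calendar time, so each has 104 − 47 = 57 weeks to come. 6 × 57 = 342 patient-weeks (6.6 patient-years); 342/780 = 44%.
- Cut at each patient's own Week 47: 780 − 6 × 47 = 498 patient-weeks (9.5 patient-years); 498/780 = 64%.
- Range if entry clusters early or late: 57/156 = 37% to 57/104 = 55% for the first cut; (104 − 47)/104 = 55% to (156 − 47)/156 = 70% for the second.

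**The case against.** A reader might infer that early deaths and withdrawals are in fact removed from the final safety and survival results. The documents do not support that.
- SAP 7 is unqualified on the as-treated set.
- Survival is an efficacy endpoint, so SAP 7.1 does not govern it. SAP 6 assigns it to the as-treated set, and SAP 6.1 words the look without the completer phrase.
- SAP 7.3 summarises adverse events causing discontinuation and lists deaths. SAP 10.4 keeps early-termination data in endpoint summaries.
- SAP 4 defines no one-year population. Its completer set is tied to T-21.
- The other looks in 7.1 are described by milestone, so the one-year phrase may be only a trigger.

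All of this stands. It makes the defect a contradiction rather than a settled exclusion, but it does not remove it. The 6.1 wording can itself be read as patients still on drug after one year, and a listing of deaths does not correct a summary percentage.

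A reader might also infer that the T-21 analysis and later follow-up have been abandoned. SAP 4.3, 6 and 6.2 specify the T-21 analysis, other SAP sections run through the end of maintenance, and nothing cancels protocol 13.2.3. What is missing is their place in the timing list.

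On size, early death may be rare. Protocol 5.1.1.3 cites about 90% survival over 12 years for patients alive six months after starting Adagen. If that applied here at a constant rate, the chance of any death among seven by Week 47 is 1 − 0.9^(7 × 0.90/12), about 5%. Withdrawals are a separate matter. The intervals in the illustrations overlap widely, and the analyses are descriptive.

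**Conclusion.** The point holds as an internal contradiction and an incomplete timing plan. SAP 7.1 conflicts with SAP 7 on who enters the final safety analysis and would permit a completer-only reading. Under that reading, one unreplaced death among six turns 83.3% survival into 100%. The look called final conflicts with protocol 13.2.3 and with the SAP's own endpoints. The 44% to 64% of exposure left out is conditional on nothing being analysed afterwards, on even entry, and on the protocol's approximate durations, which may include the lead-in.

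It would go too far to say that no patient seen in window can have a year of EZN-2279. That holds on the example calendar (Weeks 44 to 50), but not if the window applies per interval or Weeks T-5 to T-8 are repeated. The label is imprecise, and the calendar week should be stated.

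**What to change.** In SAP 6.1, 7.1 and 10.1:
1. Delete the words limiting the final analysis to subjects who complete one year. State that Week 47 is a data-cut trigger, not a population, and replace the one-year label with that week.
2. State that safety and survival use the as-treated set, with EZN-2279 summaries in all patients who received EZN-2279, including those who stopped or died. Give the survival denominator in 6.3.4 to match.
3. List the T-21 primary analysis, the Week 47 analysis, the annual analyses, and a final analysis at study completion. Keep DSMC reviews in a separate list.
4. Reconcile the BLA trigger: three subjects through T-21 in 6.4, through one year in 10.1.

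The cost is SAP wording and reruns of existing programs at the added cuts. No new data collection is needed.
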